**Table 2: Variables of the wear resistance test and levels of investigations:**

Variable	Level	Referred to
Type of material (M).	M1	Light cured nanohybrid RBC.

Time of follow-up (T).	M2	Self-cured bioactive RBC.
	T0	Immediately after restoration.
	T1	After six months.
	T2	After twelve months.
	T3	After eighteen months.
	T4	After twenty-four months.

**Table 3: Interaction between variables for wear resistance test:**

M		Type of material (M)		Total
		M1	M2	
Times (T)	T0	M1T0	M2T0	
	T1	M1T1	M2T1	
	T2	M1T2	M2T2	
	T3	M1T3	M2T3	
	T4	M1T4	M1T4	
Total		10	10	20

Sample size: n= 10

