### **3. Research Q (RQ):**

What is the difference between self cured bioactive and light cured nanohybrid (RBCs) regarding wear resistance and bioactivity after two years of clinical performance?

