#### **II-6- Evaluation of the wear resistance:**

A digital impression will be taken immediately after restoration (T0) using an intraoral scanner (Helios 600 intraoral scanner, Eighteeth, Changzhou, China). To ensure optimal performance and accuracy, the scanner underwent regular calibration before scanning each patient, following the manufacturer's recommendations. During the scanning procedure, the device will be positioned at a 90° angle for the occlusal surface and at 45° angles for both buccal and lingual surfaces. Later on, each restoration will be examined at standardized follow-up periods (Table 2 and 3); six months (T1), twelve months (T2), eighteen months (T3) and twenty-four months (T4). The 3D impressions will be analyzed using a software (Geomagic software, 3D Systems Inc., USA) program and the impressions of each two consultative visits will be superimposed to determine the wear volume loss (mm^3). (Bronkhorst et al, 2022)

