## 6- Sample size calculation:

Sample size calculation was performed using G\*Power version 3.1.9.2, (Faul *et al*, 2007) University Kiel, Germany. Copyright (c) 1992-2014.

$$f = \frac{\sigma_\mu}{\sigma}$$

[figure not shown]
$$\sigma_\mu^2 = \frac{\sum_{i=1}^k n_j (\mu_i - \mu)^2}{N}$$

Where:

$f$ : is the effect size;  $\alpha = 0.05$ ;  $\beta = 0.05$ ; Power =  $1 - \beta = 0.80$

The effect size  $d$  was **1.22 (large)** according to the previous studies (**Elderiny et al., 2024**) with alpha ( $\alpha$ ) level of 0.05 and Beta ( $\beta$ ) level of 0.05, i.e., power = 80%; the estimated sample size ( $n$ ) should be **20** samples and will be divided into **two groups**.

To account for dropouts, the sample size will be expanded by 20%, which produced 12 restorations for each group instead of 10.

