### Statistical analysis:

All collected data will be calculated, tabulated, and statistically analyzed using suitable statistical tests as follows: **A normality test:** will be done to check normal distribution for data by Shapiro-Wilk test. **Descriptive statistics:** will be calculated in the form of mean  $\pm$  standard deviation (SD), range (Max-Min). Qualitative data will be presenting as (%) frequencies (n) and percentages. **T- test or Mann-Whitney test**

**(According to the types of data).** Independent Student's T-test or Mann-Whitney will be performed for pair wise comparison between groups in each time at P value < 0.05. **The Chi-square test** will be used to test significance of association between categorical variables. **Pearson's correlation coefficient:** will be used for estimating the relationship between quantitative variables. **P<0.05** is considered significant. Statistical analysis will be performed using the computer program SPSS software for windows version 26.0 (statistical package for social science, ARMONK, NY: IBM Corp).

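### Patients lost before month 24 contribute nothing to the two-year wear comparison, because the materials are tested separately at each visit although dropout is expected

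*Protocol*

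**What the plan says.** - **Question.** Section 3 of the protocol asks how the materials differ "after two years of clinical performance".
- **Data.** Section II-6 schedules scans at T0 and at 6, 12, 18 and 24 months (T1 to T4). On the wear value it says that "the impressions of each two consultative visits will be superimposed to determine the wear volume loss".
- **Layout.** Table 3, "Interaction between variables for wear resistance test", crosses M1 and M2 with T0 to T4.
- **Dropout.** Section 6 states: "To account for dropouts, the sample size will be expanded by 20%, which produced 12 restorations for each group instead of 10".
- **Analysis.** The Statistical analysis section states: "Independent Student's T-test or Mann-Whitney will be performed for pair wise comparison between groups in each time". Its only other inferential methods are a chi-square test for categorical variables and Pearson's correlation. It names no analysis across visits.

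**The concern.** Each patient carries both materials (section II-4), so losing a patient loses a pair. Under a test done visit by visit, a patient scanned at T1, T2 and T3 but absent at T4 drops out of the comparison that answers section 3. The protocol fixes this method itself; it has not been left to a later plan.

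Two things are at stake. With at most 12 pairs, a little information already collected is unused. More importantly, the month-24 result describes only those who stayed. If loss is related to wear already seen on earlier scans, the completers' difference is biased, and the plan has nothing that would correct it. The Expected Outcomes section anticipates slightly more wear with the bioactive material. Losing the pairs where that excess is largest would hide it.

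**Working it through.** **1. The plan's own figure.** Inputs from section 6: d = 1.22, alpha 0.05, power 80%. A one-sided two-sample t-test needs 10 per group (power 83.6%; 9 per group gives 79.7%), which reproduces 20 restorations. Two-sided, 10 per group gives 73.3% and 12 give 81.5%. The dropout step is 10 × 1.2 = 12. The printed beta of 0.05 does not fit 80% power; that is a separate matter and is not used here.

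**2. Who enters the month-24 test.** If the allowance is used up, 12 − 2 = 10 patients remain. The two lost patients contribute 0 to that test, however many scans they had.

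**3. Precision if all visits are used.** The protocol gives no between-visit correlation, so ρ = 0.3 to 0.9 is assumed for the within-patient differences. With a separate mean per visit, known covariance and both losses after month 18:

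Var(month-24 mean) = σ² [(1 − R²)/10 + R²/12]

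Here R² is the squared multiple correlation of T4 on T1 to T3: 3ρ²/(1 + 2ρ) under compound symmetry and ρ² under AR(1).

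| ρ | Structure | R² | Effective n |
|---|---|---|---|
| 0.3 | AR(1) | 0.090 | 10.15 |
| 0.5 | Compound symmetry | 0.375 | 1/(0.0625 + 0.03125) = 10.67 |
| 0.7 | Compound symmetry | 0.6125 | 11.14 |
| 0.9 | Compound symmetry | 0.868 | 11.69 |

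The standard error relative to 10 completers is √(10/effective n), about 0.99 down to 0.925. If one patient is lost after month 6 and one after month 12, the effective n is 10.0 to 11.6. With no dropout it is 12 either way, so earlier visits add no precision at month 24.

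**4. Bias if loss follows wear already seen.** Suppose the 2 of 12 with the largest T3 difference are lost. For a standard normal truncated above its 10/12 quantile (0.967), the mean is −0.2499/0.8333 = −0.300. The completers' T4 mean then shifts by −0.300ρ: −0.15, −0.21 and −0.27 SD for T3-T4 correlations of 0.5, 0.7 and 0.9. Taking exactly the top 2 of 12, the simulated shifts are −0.13, −0.19 and −0.25 SD. Regressing on T3 brought these to within 0.003 SD of zero. This loss pattern is an assumed adverse case; the protocol does not predict it.

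**5. Power of a wear-rate analysis.** Assumptions, in units of mean two-year loss: patient SD 0.20, tooth SD 0.22, true difference 0.30, scan error SD e on every scan, linear wear, 2 of 12 lost after T2. The paired T4 difference has SD √[2(0.22² + 2e²)] = 0.327, 0.370 and 0.507 for e = 0.05, 0.10 and 0.20. The standardised differences are 0.92, 0.81 and 0.59, and with n = 10 the power is 73%, 63% and 39%. Simulation agrees:

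| e | Plan's unpaired test at T4 | Paired test at T4 | Paired test on rates, all scans |
|---|---|---|---|
| 0.05 | 57% | 74% | 81% |
| 0.10 | 48% | 63% | 69% |
| 0.20 | 32% | 38% | 42% |

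Across runs, the gain of rates over the paired T4 test is about 3 to 8 points. The larger step, from the unpaired to the paired test, comes from respecting the pairing and not from the extra visits.

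**6. Which model.** A model with random patient and tooth intercepts only assumes equal variance at T1 to T4. If restorations differ in wear rate, variance grows with time and the pooled standard error is too small at T4. With the same tooth SD, linear wear, 12 pairs and no true difference, the type I error of the T4 contrast was about 16%, 12% and 8% for the three scan errors. The paired T4 test held 5%.

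**7. Rate versus month-24 difference.** If loss follows √t with two years as t = 1, the least-squares slope is 1.41 over T0 to T2 and 0.95 over T0 to T4. Patients lost early would then contribute a different quantity.

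**The case against.** A comparison of materials at month 24 is a legitimate answer to section 3, and section 6 already deals with dropout by enrolling 12 to keep 10. That stands as regards numbers. Enrolling more patients does not, however, protect against selective loss.

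A reader might infer three stronger things that the documents do not support.

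- *That Table 3 promises an interaction test the analysis fails to deliver.* Table 5 carries the same kind of title for bioactivity, and both tables list cells and sample sizes. The word labels a crossed layout. The hypothesis and objectives ask only whether the materials differ, so leaving out a test of a widening gap is no fault.
- *That the T1 to T3 scans are wasted.* This is true of the statistical test but perhaps not of the measurement. If *consultative* in section II-6 means consecutive, the T3 scan is the reference for the T4 value, and a two-year total would be summed through T1 to T3.
- *That any longitudinal model brings a sizeable gain.* The power gain in step 5 belongs to a rate comparison, which is not equivalent to the month-24 difference. Without dropout, the visit-factor model gains nothing at T4. A random-intercept model would make the inference worse.

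**Conclusion.** The point holds in a limited form. The stated visit-by-visit test excludes from the two-year wear comparison every patient lost before month 24, in a plan that expects such losses. The main benefit of change is protection against bias when dropout depends on wear already observed: about 0.15 to 0.27 SD in an assumed adverse case with 2 of 12 lost. That protection needs loss to depend only on what was observed.

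The precision gain is modest: 0 to 1.7 of the 2 lost patients recovered, and nothing without dropout. All sizes rest on assumed correlations, variances and timing of loss, because the protocol gives none. This is a worthwhile improvement at low cost; it does not invalidate the trial.

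**What to change.** 1. In section II-6, define wear at each visit as cumulative loss from T0. The text leaves T0-T4 versus T3-T4 unclear, and summing consecutive intervals would fail after one missed scan.
2. In the Statistical analysis section, replace the visit-by-visit wear tests by one repeated-measures model that keeps the pairing. For example, model the within-patient M2 minus M1 differences at T1 to T4 with visit as a factor, an unstructured or heterogeneous (time-varying) covariance and small-sample degrees of freedom. Do not use random intercepts alone.
3. Report the month-24 M2 minus M1 difference with its 95% CI as the two-year result.
4. Optionally, add a within-patient comparison of per-restoration wear rates from all scans as a supportive analysis, stating that it is a different quantity if wear slows.

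**Cost.** No extra patients, visits or scans are needed, and the analysis can be run in the SPSS already named. The drawback is a covariance estimated from only 12 patients: an unstructured 4 × 4 matrix has 4 × 5/2 = 10 parameters. A simpler heterogeneous structure should therefore be named in advance as the fallback.

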**Table 4: Variables of the bioactivity test and levels of investigations:**

Variable	Level	Referred to
Type of material (M).	M1	Light cured nanohybrid RBC.
	M2	Self-cured bioactive RBC.
Time of follow-up for mineral density (D).	D0	Immediately after restoration.
	D1	After one month.
	D2	After three months.

**Table 5: Interaction between variables for bioactivity test:**

M		Type of material (M)		Total
		M1	M2	
Times (D)	D0	M1D0	M2D0	
	D1	M1D1	M2D1	
	D2	M1D2	M2D2	
Total		10	10	20

Sample size: n= 10

## 6- Sample size calculation:

Sample size calculation was performed using G\*Power version 3.1.9.2, (Faul *et al*, 2007) University Kiel, Germany. Copyright (c) 1992-2014.

$$f = \frac{\sigma_\mu}{\sigma}$$

[figure not shown]
$$\sigma_\mu^2 = \frac{\sum_{i=1}^k n_j (\mu_i - \mu)^2}{N}$$

Where:

$f$ : is the effect size;  $\alpha = 0.05$ ;  $\beta = 0.05$ ; Power =  $1 - \beta = 0.80$

The effect size  $d$  was **1.22 (large)** according to the previous studies (**Elderiny et al., 2024**) with alpha ( $\alpha$ ) level of 0.05 and Beta ( $\beta$ ) level of 0.05, i.e., power = 80%; the estimated sample size ( $n$ ) should be **20** samples and will be divided into **two groups**.

To account for dropouts, the sample size will be expanded by 20%, which produced 12 restorations for each group instead of 10.

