#### Methodology:

Twelve healthy patients with 24 carious molar teeth will be selected where each patient should have two ocluso- mesial cavities. Standardized

occluso- mesial cavities will be prepared for all the selected teeth, for each patient the first tooth will be restored with conventional nanohybrid RBC (M1). Meanwhile, the second tooth will be restored by self-cure bioactive RBC (M2). Then, wear resistance will be evaluated by intraoral scanner immediately after restoration (T0), six months later (T1), after 12 months (T2), 18 months (T3) and 24 months (T4). Software analysis will be done by superimposing the 3D digital impression and evaluate the restoration wear by calculating the 3D volume loss.

Also, bioactivity of the restoration will be measured by measuring the mineral density beneath the restoration. Digital radiographic images will be taken for the restoration by parallel technique and grey scale of the pixels under restoration will be measured by software immediately after restoration (D0), one month later (D1) and after 3 months (D2).

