### **4. Research Hypothesis, Aim, Objectives & Expected Outcomes**

#### **a. Hypothesis**

Null hypothesis: There is no significant difference between wear resistance and bioactivity between self cured bioactive RBC and light cured nano-hybrid one.

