#### **d. Expected Outcomes**

Self cured bioactive RBC could show slight lower wear resistance than light cured nano-hybrid RBC with remarkable bioactive potential.

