### **II-4 Randomization:**

To minimize selection bias and ensure equal distribution of treatment protocol across both treated molars, simple randomization will be used to randomly determine which molar receives which material. Therefore, randomization will be performed using an online randomization tool (<https://www.randomizer.org/>) prior to treatment allocation where, each patient will be given a unique study number, ensuring that each patient receives both treatments in a randomly assigned manner.

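### Section 6 pairs beta = 0.05 with 80% power, which cannot both hold, and its 10 per group gives 80% power at d = 1.22 only under an undeclared one-sided test

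*Protocol*

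**What the plan says.** The Sample size calculation (Protocol, section 6) lists alpha = 0.05, beta = 0.05 and power = 1 − beta = 0.80. The sentence below the list repeats the pair, giving the beta level and then the power: "level of 0.05, i.e., power = 80%; the estimated sample size". The effect size is labelled d, is set at 1.22 and is attributed to an earlier study. The formula printed above it, however, defines the analysis-of-variance effect size f. The result is 20 samples in two groups, raised by 20% for dropout, "which produced 12 restorations for each group instead of 10". No test and no sidedness are named there.

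Four other places bear on how to read this:

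- Section 4a states a null without direction: "There is no significant difference between wear resistance and bioactivity between self cured bioactive RBC".
- Section 4d expects a direction for wear: "Self cured bioactive RBC could show slight lower wear resistance than light cured nano-hybrid RBC". It declares no one-sided test.
- Section II-4 makes the design within-patient, "ensuring that each patient receives both treatments in a randomly assigned manner".
- The Statistical analysis section plans an unpaired comparison, an independent "T-test or Mann-Whitney will be performed for pair wise comparison between groups in each time", also without sidedness.

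**The concern.** Alpha, beta, power and d are the whole stated basis for the size of this trial. One of the two error figures must be wrong, and a reader cannot tell from the text alone which was used.

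The remaining inputs do not fix the answer either. Depending on whether the test is one- or two-sided, and on whether 1.22 is a between-group difference, a paired difference or an f, the same inputs give totals from 8 to 38 restorations. If the authors intend the usual two-sided test on independent groups, 10 per group falls short of 80%, and the two extra patients per group are needed to reach the target rather than to cover losses over 24 months of follow-up.

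The calculation also treats the restorations as two separate groups, although they are pairs within patients. The power of the within-patient comparison that the design provides is not given at all.

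**Working it through.** **Inputs.** From section 6: alpha 0.05; beta 0.05; power 0.80; d = 1.22; 10 per group; 12 per group after the 20% increase. The within-patient correlation r is not in the protocol, so it is an assumption here and a range is shown.

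**Beta and power.** Power = 1 − beta. With beta = 0.05, power = 0.95. With power = 0.80, beta = 0.20.

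**Reproducing the 20.** For a t-test on two independent samples, df = 2n − 2 and the noncentrality is d√(n/2). At n = 10 this is 1.22 × √5 = 2.73 on 18 df; at n = 12 it is 1.22 × √6 = 2.99 on 22 df. Power from the noncentral t distribution at alpha 0.05:

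| Evaluable per group | One-sided | Two-sided |
|---|---|---|
| 9 | 79.7% | – |
| 10 | 83.6% | 73.2% |
| 11 | – | 77.7% |
| 12 | 89.4% | 81.5% |

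Total restorations needed under each reading:

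| Reading of the inputs | 80% power | 95% power |
|---|---|---|
| Independent, one-sided | 20 | 32 |
| Independent, two-sided | 24 | 38 |
| f = d/2 = 0.61, two-group F test | 24 | 38 |
| 1.22 taken as f | 8 | – |
| 1.22 taken as a paired dz, two-sided | 16 (8 pairs) | 22 (11 pairs) |

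The F test on two groups is the two-sided t-test, so its entries match that row. Only the one-sided independent test at 80% gives exactly 20. A two-sided normal approximation gives 11 per group, or 22. No independent-sample reading at beta = 0.05 comes near 20.

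**Dropout margin.** 10 × 1.2 = 12, which covers two losses. Two-sided on independent samples, 12 is already the minimum for 80%, so one loss per group brings power to 77.7% and two bring it to 73.2%.

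**Power for pairs.** For a two-sided paired t-test, df = n − 1 and the noncentrality is dz√n.

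- If 1.22 is dz: 92.8% with 10 pairs, 97.0% with 12.
- If 1.22 is a between-group d: dz = d/√(2(1 − r)), which is 0.86 at r = 0, 1.03 at r = 0.3 and 1.22 at r = 0.5.

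| Assumed r | 10 pairs | 12 pairs |
|---|---|---|
| 0 | 68% | 78% |
| 0.3 | 83% | 90% |
| 0.5 | 93% | 97% |

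The dz that gives 80% power is 0.996 for 10 pairs and 0.889 for 12. Solving r = 1 − (1.22/dz)²/2 gives r of about 0.25 and 0.06.

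**The unpaired test as planned, applied to paired data** (two-sided, 400,000 simulated trials, 1.22 as a between-group d). With 10 pairs, power is 76.6% at r = 0.3, 79.5% at r = 0.5 and 80.4% at r = 0.55. With 12 pairs, it is 81.4% at r = 0 and 88.5% at r = 0.5.

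**The case against.** The best defence is that 20 is not a wrong sum. It is exactly what a one-sided independent t-test at 80% power requires, so the 73% depends on a two-sided test that the protocol never states. This stands as far as it goes: the fault is an undeclared sidedness set against a non-directional null, not a miscalculated n.

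It can also be said that the meaning of 1.22 is fairly clear. Section 6 calls it d, cites a source and speaks of two groups, and the Statistical analysis section names an independent t-test, so a between-group difference is the natural reading and nothing in the text points to a paired dz. That reading is indeed the more likely one. But the printed formula is for f, neither the outcome nor the time point behind 1.22 is given, and under this reading the within-patient power depends on a correlation that the protocol does not supply.

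Third, the practical shortfall is limited. At the planned 12 per material even the two-sided independent calculation gives 81.5%, and with pairs a correlation of about 0.25 is enough for 80% at 10. This is correct, and it is why no increase in enrolment is asked for.

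Finally, the choice of an unpaired test for a paired design is an analysis question in its own right. It matters here only because the power statement and the test should describe the same comparison. None of these points touches the contradiction between beta and power.

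**Conclusion.** The point holds. Beta = 0.05 with power = 80% is impossible by the protocol's own formula, appears twice, and needs no assumption to show. Beta 0.05 is most likely a slip for 0.20, because 20 restorations fit 80% and not 95%.

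The claimed 80% at 10 per group, d = 1.22 and alpha 0.05 is met one-sided (83.6%) and missed two-sided (73.2%) for independent samples. With no one-sided test declared and a non-directional null, the two-sided figure is the one a reader would apply. For the within-patient comparison, power with 10 evaluable patients is between 68% and 93% over assumed correlations of 0 to 0.5 if 1.22 is a between-group d, and 92.8% if it is a paired dz. The trial is therefore not shown to be underpowered; its stated power is unsupported as written. This should be corrected before the protocol is relied on, and the correction does not affect enrolment.

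**What to change.** In section 6:

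1. Write beta = 0.20 in the symbol list and in the sentence.
2. Name the test and declare it two-sided.
3. Say whether 1.22 is a between-group d or a paired dz, and for which outcome and time point. Remove the f formula or replace it with the one used.
4. Restate the power for pairs, for example: *Two-sided paired t-test, alpha 0.05, beta 0.20: 10 evaluable patients have 80% power for a paired effect dz of about 1.00 (12 patients: 0.89). Twelve patients are enrolled to allow for two losses.* These effects are solved from the available n, so the text should also say how 1.22 compares with them. If 1.22 is a between-group d, give the assumed within-patient correlation.

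In the Statistical analysis section, name the paired test that matches this calculation.

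The cost is wording only, with no extra patients. The stated power may look less favourable if 1.22 is a between-group d and the correlation is low.

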### Statistical analysis:

All collected data will be calculated, tabulated, and statistically analyzed using suitable statistical tests as follows: **A normality test:** will be done to check normal distribution for data by Shapiro-Wilk test. **Descriptive statistics:** will be calculated in the form of mean  $\pm$  standard deviation (SD), range (Max-Min). Qualitative data will be presenting as (%) frequencies (n) and percentages. **T- test or Mann-Whitney test**

**(According to the types of data).** Independent Student's T-test or Mann-Whitney will be performed for pair wise comparison between groups in each time at P value < 0.05. **The Chi-square test** will be used to test significance of association between categorical variables. **Pearson's correlation coefficient:** will be used for estimating the relationship between quantitative variables. **P<0.05** is considered significant. Statistical analysis will be performed using the computer program SPSS software for windows version 26.0 (statistical package for social science, ARMONK, NY: IBM Corp).

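### The choice between t-test and Mann-Whitney appears to be left to a normality check on 10 to 12 values per group, with nothing holding the test constant across visits (minor)

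*Protocol*

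**What the plan says.** The protocol, under Statistical analysis, lists a normality check that "will be done to check normal distribution for data by Shapiro-Wilk test". It then gives two candidate tests with the selector "According to the types of data", and states: "Independent Student's T-test or Mann-Whitney will be performed for pair wise comparison between groups in each time at P value < 0.05". It names no default test, no level for the Shapiro-Wilk test, no statement of which values are checked, and no requirement to use one test throughout.

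The sample size section sets 20 restorations in two groups and adds 20% for dropout, "which produced 12 restorations for each group instead of 10". The abstract, Randomization and Restorative procedures sections give every patient both materials, one per molar. Wear volume loss is measured at 6, 12, 18 and 24 months. Mineral density is measured immediately after restoration and at one and three months. Both outcomes are continuous.

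**The concern.** Because both outcomes are continuous, the type of data cannot separate a t-test from a Mann-Whitney test. The only listed item that can is the Shapiro-Wilk result. The natural reading is therefore that the outcome data pick the test. If that reading is wrong, the section contains no usable selection rule at all.

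Three things follow:

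- A check on 10 to 12 values is a weak instrument for this decision.
- Because the comparison is made visit by visit, wear at 12 months could be judged on means and wear at 18 months on ranks on account of one odd value.
- In a two-teeth-per-patient design the relevant distribution is that of the within-patient difference. A check on each material's raw values looks at the wrong quantity.

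**Working it through.** **Inputs.** From the protocol: 20 restorations in two groups give 20 / 2 = 10 per group, and 10 × 1.2 = 12 per group after the dropout allowance, as stated. There are four wear visits after baseline. The test level is 0.05, and the effect size is d = 1.22. Assumed, because the protocol gives none: Shapiro-Wilk at 0.05, run on each material at each visit, with Mann-Whitney used if either material is flagged; normal or lognormal shapes; and the correlations named below.

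**1. What the check detects** (10,000 simulated samples per shape). Share of single groups flagged:

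| Shape | n = 10 | n = 12 |
|---|---|---|
| Normal (false flag) | 5.2% | 4.6% |
| Lognormal, sigma 0.4 (skewness 1.3) | 17% | 22% |
| Lognormal, sigma 0.5 (skewness 1.75) | 24% | 30% |
| Lognormal, sigma 0.75 | 44% | 52% |
| Lognormal, sigma 1 | 61% | 70% |

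At sigma 0.4 to 0.5 the check therefore misses 70 to 83% of samples. At sigma 1 it catches most of them.

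**2. Mixed tests over four wear visits.** Let q be the chance of a switch at one visit. With independent visits, P(mixed) = 1 − (1 − q)⁴ − q⁴.

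- Normal data: q = 1 − 0.95² = 0.0975. P = 1 − 0.9025⁴ − 0.0975⁴ = 1 − 0.6634 − 0.0001 = 0.337.
- Lognormal sigma 0.5, n = 10: q = 1 − (1 − 0.242)² = 0.425. P = 1 − 0.109 − 0.033 = 0.858.

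Simulation with between-visit correlation 0, 0.5 and 0.8 gave 30 to 35% for normal data and 66 to 88% for lognormal sigma 0.5. Across all lognormal settings tried (sigma 0.25 to 0.75) the range was 45 to 88%.

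**3. Type I error of check-then-test** (20,000 trials, independent groups, normal and lognormal sigma 0.5). Check-then-test: 5.0 to 5.3%. Always t: 4.5 to 4.9%. Always Mann-Whitney: 4.3 to 4.5%. There is no material inflation.

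**4. How often the switch changes the t-test verdict.** About 1% or less with normal data. With lognormal sigma 0.5 and a moderate to large effect, about 5 to 11%, depending on how the effect is specified.

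**5. Raw values against differences.** With skewed pairs (sigma 0.5 to 0.75, within-patient correlation 0.5, n = 10), at least one raw group is flagged in 41 to 68% of trials. The within-patient differences are flagged in 14 to 25%.

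**6. What a fixed paired test gives.** At n = 10, correlation 0.5, normal data and a 1 SD shift, the plan's rule has about 1% type I error and 57% power. The paired t-test has about 5% and 80%.

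At the protocol's d = 1.22 and n = 10, two-sided, the unpaired t-test has noncentrality 1.22 × √(10/2) = 2.73 and 73.2% power. The paired test uses 1.22 / √(2(1 − r)) × √10. Its power is 68.1% at r = 0, 82.6% at r = 0.3 and 92.8% at r = 0.5.

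**The case against.** Four objections deserve weight.

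- **The rule is inferred.** The protocol does not write that Shapiro-Wilk decides, that it is run at each visit, or that it uses raw values. The phrase about each time attaches to the comparison, not to the check, and one check with one test per outcome would also fit the text. This stands, so the per-visit figures are conditional. Which values are checked, and at what level, may properly sit in a statistical analysis plan and is not faulted here. What remains is that the protocol itself offers two tests without fixing either.
- **Error control is sound.** A reader might infer that a data-driven choice must raise the false-positive rate. Step 3 shows that it does not, under the shapes tried.
- **The check is not blind.** A reader might conclude that it misses most skew of any kind. It does not: strong skew is usually caught, and more often still if either group can trigger the switch. The miss rate applies to mild to moderate skew.
- **Most of the gain comes from pairing.** This also stands. Replacing the unpaired tests accounts for most of the power difference in step 6. Yet moving to a choice between paired t and signed-rank would leave the switch in place, so the point does not vanish with pairing alone.

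A reader might also compute 1 − 0.95¹⁴ = 51% as the chance of a false flag somewhere across 14 group-by-visit checks. That figure should not be used. The checks share patients and are not independent, and the count pools two unrelated outcomes and includes the baseline density reading.

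**Conclusion.** The concern holds in a limited form, and it is minor. The section names two tests and appears to let a weak check on the outcome data choose between them, with nothing keeping the choice constant across visits. If the check is applied per group and visit, about 30% of trials with normal data, and more with skewed data, would mix methods over the four wear visits. The harm is inconsistent analysis, a choice made after seeing outcomes, and a check on a quantity that is not the relevant one in this design. It is not inflated type I error. The shapes, correlations and either-group trigger are assumptions. The sizes move with them, but the absence of a fixed test does not.

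**What to change.** In Statistical analysis, replace the sentence that offers an independent t-test or Mann-Whitney with wording such as: *For each outcome and each visit, the materials will be compared by a two-sided paired t-test on the within-patient difference (M2 minus M1). The Wilcoxon signed-rank test will always be reported as a sensitivity analysis. Shapiro-Wilk and plots of the differences will be descriptive and will not select the test.* Two-sided testing matches the stated null hypothesis of no difference.

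Make the change before any outcome data are examined, and together with the correction of the unpaired analysis, since one sentence serves both. It needs no extra patients, data or software. The costs are the freedom to switch and some power if the two teeth of a patient are nearly uncorrelated: 68.1% against 73.2% at n = 10 and d = 1.22. In simulation (lognormal sigma 0.5, n = 10, correlation 0 to 0.5) the fixed paired t and signed-rank tests kept type I error at 4.2 to 5.0% without any pre-test.
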